### 7.2 Subject Participation and Study Duration

All subjects will be followed for the primary endpoint, and at subsequent follow-up visits, according to the approved INTERMACS® protocol and using data from INTERMACS®.

Data collection for analysis and subject status for inclusion in analyses will be assessed as follows:

- Subjects who have been transplanted prior to month 6 post implant will be considered complete at the time of the primary endpoint visit time-point.
- Subjects, who have a device exchange prior to month 6, will be evaluated according to the original implant date.

- Subjects who remain on device support after the primary endpoint time-point, either the original device or exchange device, will be followed according to the INTERMACS® protocol until transplant, or until 2.5 years post implant of the original device. A subject's study participation is considered complete at either the time of at induction of anesthesia for transplant, or at the 2.5 year post implant visit.
- Subjects who have been explanted for recovery prior to month 6 will be followed until their next scheduled follow-up visit according to the INTERMACS® protocol, at which time their participation in the study is considered complete.
- The per-protocol analysis population will include those thoracotomy subjects with the outflow in the ascending aorta only. As a result, enrollment may exceed sample size requirements.
- The per-protocol analysis population will include those thoracotomy subjects with the procedure performed on-pump only. As a result, enrollment may exceed sample size requirements.

Subject data will be evaluated for a maximum of 2.5 years.

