### 9.2.8 Additional data collection

#### Post-Transplant

Additional information will be collected to evaluate the effect of the lateral surgical procedure on the pre and post-operative requirements, length and severity of the hospitalization during the procedure and length of hospitalization post-transplant.

The following parameters will be included:

1. Total operative time
2. Cardiopulmonary Bypass time
3. Intraoperative blood/ coagulation products
4. If the surgical procedure was done on a Virgin Chest
5. If the patient had Pneumothorax
6. Severity of pericardial/pleural adhesions
7. Time on ventilator/inotropes
8. Total Days on Intensive Care Unit
9. Total Days in Hospital after transplant

The additional data will be collected on transplanted patients only.

The additional data will not be captured in INTERMACS database.

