#### Follow-Up after stroke if transplanted or explanted

Additional information will be collected for all stroke patients who are transplanted or explanted in order to assess mRS ( $\geq 3$  months post-stroke) to classify them for the primary endpoint.

The following parameters will be included:

1. Date of assessment
2. mRS

The additional data will be collected only on transplanted or explanted patients who had a stroke with mRS  $\geq 4$  less than 3 months prior to the transplant or explant.

The additional data will not be captured in INTERMACS database.

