### 11.4 Handling of Missing Outcomes

Every effort will be made to gather all data associated with the primary, secondary and additional endpoints. A complete case analysis, which includes all subjects with complete follow up will be conducted as the primary analysis of the primary endpoint.

[REDACTED]

[REDACTED]

[REDACTED]

- [REDACTED]
- [REDACTED]
- [REDACTED]

[REDACTED]

[REDACTED]

If a subject experiences a stroke and subsequently completes the 6 month follow-up, a post-stroke (greater than 6 months post-event) mRS is still required. If the subject dies prior to the post-stroke mRS but after the 6 month follow-up, the outcome will be considered a failure.

For the secondary endpoint, imputation for missing data regarding duration of hospital stay (in days) will not be performed.

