##### Follow-up

All patients will be followed as long as an MCSD is in place. If a patient has an MCSD removed and is not transplanted, then the patient will be followed for 1 year. Vital

status, including transplantation and survival, will be determined during this year. If a patient transfers his/her care to another hospital, the patient is deactivated at the implanting hospital at the time of transfer and is re-activated at a new center provided the new center is an INTERMACS®-participating center. The patient transfer process can be found in the MOP, Section 4.4.

If a patient has an MCSD removed and is transplanted, then the patient is no longer followed in INTERMACS®. At that time, the patient becomes part of the **Organ Procurement and Transplant Network (OPTN)** transplant database and will be followed by that database. A patient undergoing transplantation more than 1 year after MCSD explantation with no re-implant will be followed in INTERMACS® for the first year after explant to determine if they have undergone transplantation or died. If the patient undergoes a transplant, then he/she will be followed through the OPTN database at the time of transplantation.

[figure not shown]

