2.4.1. Primary Endpoint

The primary endpoint is success at 6 months for all enrolled and implanted subjects. Success is defined as follows:

- Alive on the originally implanted device at 6 months, and the subject has not had a severe stroke; or
- Transplanted by Month 6, and the subject has not had a severe stroke prior to transplant; or
- Explanted for recovery by Month 6, and the subject has not had a severe stroke prior to explant for recovery.

All subjects with stroke events from implant to Month 6 will be required to remain in study follow-up until the post-stroke mRS measure (≥ 3 months post stroke event) is obtained, even if this occurs at the next expected follow-up visit. If a stroke subject is alive at 6 months, but dies before the post-stroke mRS is obtained, the subject will be considered a failure with regard to the primary endpoint.

A stroke is considered severe if either:

- The first mRS score assessed ≥ 3 months post stroke event is ≥ 4 ; or

- The follow-up (≥ 3 months post stroke event) mRS score is missing and the day-of-event mRS is ≥ 4 .

Specifically, any subject experiencing any of the following events will be considered a failure:

- Death by any cause prior to 183 days post-implant and prior to transplant or explant for recovery
- A severe stroke occurring prior to 183 days post-implant and prior to transplant or explant for recovery
- A stroke followed by death within 91 days post-event occurring prior to 183 days post-implant and prior to transplant or explant for recovery

Subjects with a stroke with no available mRS and no death ≥ 91 days post-stroke occurring prior to 183 days post-implant and prior to transplant or explant for recovery will be considered missing in the primary analysis.

All subjects with at least 182 days of documented follow-up without meeting any of the above failure criteria will be considered a success. Subjects not considered a success or a failure will be excluded from the analysis.

N.B. As INTERMACS only includes visits every 6 months starting at the 6 month visit, it should be noted that should a stroke occur after 3 months, a post-event mRS score may not be obtained until the 12 month visit.

Hypotheses:

$$H_0: \pi_T \leq 77.5\%$$

$$H_a: \pi_T > 77.5\%$$

where π_T = the proportion of the patient population experiencing success for the Thoracotomy group.

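### Does the 182-day success rule in SAP 2.4.1 drop subjects transplanted before Month 6 from the primary analysis?

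*SAP*

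**What the plan says.** SAP 2.4.1 classifies subjects in two layers. The first is the endpoint definition, with three routes to success. The second route reads: "Transplanted by Month 6, and the subject has not had a severe stroke prior to transplant". The first is survival on the original device, and the third is explant for recovery.

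The second layer is operational. It lists failure events (death, severe stroke, stroke followed by death within 91 days), each counted only if it comes before transplant or explant for recovery. It sets aside as missing certain stroke subjects with no modified Rankin score. It then says: "All subjects with at least 182 days of documented follow-up without meeting any of the above failure criteria will be considered a success". The last line is: "Subjects not considered a success or a failure will be excluded from the analysis".

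The protocol bears on this in three places:

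- Section 7.2: "Subjects who have been transplanted prior to month 6 post implant will be considered complete at the time of the primary endpoint visit time-point".
- Section 11.4: "A complete case analysis, which includes all subjects with complete follow up will be conducted as the primary analysis of the primary endpoint".
- Appendix A, adult registry follow-up: "If a patient has an MCSD removed and is transplanted, then the patient is no longer followed in INTERMACS".

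Section 9.2.8 adds some data outside the registry. For transplanted subjects these concern the transplant operation and hospital stay, including "Total Days in Hospital after transplant". A later Rankin score is collected only for a subset with a recent severe stroke ("The additional data will be collected only on transplanted or explanted patients who had a stroke with mRS" of 4 or more).

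**The concern.** The operational lines run failure, missing, success, everyone else out. That looks like a complete algorithm, and a programmer could code it without the bullets above it. The failure items mention transplant; the success sentence does not. Documented follow-up is not defined.

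Take a subject transplanted at day 90 with no stroke. No failure item applies. Registry follow-up has ended, and the extra post-transplant data need not reach day 182. On the operational lines alone this subject is neither success nor failure and leaves the denominator. On the definition bullets the subject is a success.

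In a bridge-to-transplant study, early transplant is a main route to success. Removing such subjects takes away only successes. It lowers the observed rate and shrinks the sample below the 145 on which the power rests, so the two codings could give opposite conclusions from the same data.

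**Working it through.** **1. The plan's own figure.** Inputs from SAP 2.1.1: true success 86%, goal 77.5%, exact binomial test, one-sided alpha 0.05, N = 145. The pass mark is the smallest x with P(X ≥ x | 145, 0.775) ≤ 0.05.

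- x = 121, with exact size 4.94%.
- Power = P(X ≥ 121 | 145, 0.86) = 84.3%.
- Exact power rises and falls with n (79.2% at 144). From 145 upward it stays at or above 80%, so the stated sample size reproduces.

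**2. The passages side by side, for a stroke-free transplant at day 90.**

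| Text | Result |
|---|---|
| SAP 2.4.1 definition, second route | success |
| SAP 2.4.1 failure list | not a failure; every item stops at transplant |
| SAP 2.4.1 182-day sentence | silent; it names a group who are successes and does not say only that group |
| SAP 2.4.1 exclusion sentence | does not apply; the subject is already a success |
| Protocol 7.2 | complete for the primary endpoint |
| Protocol 11.4 | complete subjects are in the primary analysis |
| Protocol 2, 6.3, 11.1.2 and SAP 1.2 | transplant by Month 6 is a route to success |

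No line makes this subject a failure or sends the subject out. Exclusion arises only if the definition is set aside and the 182-day sentence is treated as the sole route to success. Under the reading that uses every line, the design in step 1 is unchanged.

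**3. Size of the misreading, if it happened.** The documents give no early-transplant share f for this study, so f is assumed. The largest value shown is 37/140 = 26.4%, the proportion alive after transplant at day 180 in the earlier US trial (Protocol 4.2.3). It is a reference value, not an upper bound. Assume also that no early-transplant subject has 182 documented days, which is the worst case.

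The number analysed is m ~ Binomial(145, 1 − f). The success probability among them is (p − f)/(1 − f). For f = 37/140 and p = 0.86 this is (0.860 − 0.264)/(1 − 0.264) = 0.810, with 145 × 0.736 ≈ 107 analysed. The exact test is applied at each m and averaged.

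| f | Mean analysed | Power at true 86% | Rejection at true 77.5% |
|---|---|---|---|
| 0 | 145 | 84% | 4.9% |
| 5% | 138 | 72% | 2.0% |
| 10% | 131 | 60% | 0.8% |
| 15% | 123 | 46% | 0.3% |
| 20% | 116 | 32% | 0.1% |
| 26.4% | 107 | 18% | 0.02% |

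**4. Could the misreading reverse a result?** One-sided 95% exact lower limits:

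- 125/145 = 86.2%, lower limit 80.6%: goal met.
- 20 early transplants removed: 105/125 = 84.0%, lower limit 77.6%: met.
- 21 removed (21/145 = 14.5%): 104/124 = 83.9%, lower limit 77.4%: not met.

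The number that must be removed depends on the starting count: 31 (21%) from 127/145, and 47 (32%) from 130/145.

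**The case for a change.** The best case for a change is that clear intent does not make a rule unambiguous. The operational lines are laid out as if exhaustive, the word that opens them presents them as the specific form of the definition, and the success sentence omits an exception that each failure item carries. Even a 5% early-transplant share takes power below 80% under the misreading. The repair would be one clause, and the transplant dates are already collected.

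Part of this stands. The success sentence is incomplete as a stand-alone rule, documented follow-up is undefined, and the arithmetic is right. But it measures a coding error, not something the plan instructs. To make that error an analyst must overlook the definition in the same section, the repeated endpoint wording in both documents, and the completeness rule in Protocol 7.2. In a bridge-to-transplant study, a primary analysis that lost its transplanted subjects would also be hard to miss in the disposition tables.

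Two related matters do not alter this. Explants for recovery have no clause in the 182-day sentence either, but they are also in the definition, and the registry follows them for a year. Device exchange is absent from the failure list; that is a separate point with a different direction of error. Combining the two would mix an anti-conservative problem into one that is conservative by itself.

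**Conclusion.** No change follows. Read together, SAP 2.4.1 and Protocol 7.2 and 11.4 already code a subject transplanted by Month 6 without an earlier severe stroke as a success and keep that subject in the denominator. The exception is a subject whom the SAP separately classes as missing because of a stroke with no Rankin score. The silent success sentence is a missing cross-reference that a competent analyst fills from the definition just above it.

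On that reading the effect on the design is nil: 121 of 145 needed, size 4.94%, power 84.3%. The fall in power to between 72% and 18% needs three things: the definition is ignored, the early-transplant share lies between an assumed 5% and 26.4%, and no transplanted subject has 182 documented days. Even then the error runs against the sponsor. Rejection at a true 77.5% falls below 4.9%, so this point alone cannot create a false positive.

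The conclusion rests on the visible text. Parts of Protocol 11.4 and SAP 2.4.7 are redacted and are not counted for either side.

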2.4.2. Secondary Endpoint

The secondary endpoint is improvement in the length of initial hospital stay (initial recovery and step down unit) for all enrolled and implanted subjects, which is calculated by considering the number of days in acute care (ICU/CCU) plus the number of days in intermediate/step-down care (both variables taken as reported directly by INTERMACS), comprising the total number of days post-implant to discharge.

It is estimated that the mean length of initial hospital stay is 26.1 days for median sternotomy patients and thus the relevant hypotheses for this endpoint for each cohort are given by

$$H_0: \mu_T \geq 26.1$$

$$H_a: \mu_T < 26.1$$

where μ_T = the mean length of initial hospital stay for the Thoracotomy Implant Technique of the HVAD.

This secondary endpoint will be calculated and tested for each cohort using an upper tail one-sided t-test at 0.05 level of significance. Due to the skewed nature of this data, a one-sample sign test with an upper tail one-sided level of confidence of 0.05 will be conducted as supportive analysis.

The number and percentage of subjects with re-hospitalization after the initial hospitalization will be tabulated. Cumulative length of re-hospitalization after initial hospital stay (LOS) overall will be summarized using descriptive statistics, including 95% confidence intervals for the means.

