The Quality of Life (QoL) determined from KCCQ Overall Summary Score for the subset of 70 patients who had data at both baseline and Month 6 showed a 31 point improvement over the 180 day period. In addition, as measured by the EQ-5D Visual Analog Scale, 72 subjects who had both baseline and 180 day data showed an improvement of 29.5 points over the 180 day period. Functional analyses showed similar improvements. At baseline 133/139 subjects (96%) were classified as NYHA class IV. A Discharge visit was conducted for 128 patients (median duration of hospital stays was 19 days), and data on NYHA was available for 85/128, (66.3%) of these patients, data on 43 was not collected. At discharge, 4/85 (4.7%) were NYHA Class I, 47/85 (55%) of subjects were class II, 26/85 (30.6) Class III and 8/85 (9.4%) Class IV. For the 6-minute walk test, data collected at baseline and month 6 showed similar improvements in functional capacity. A total of 88 patients were still supported on the device at 6 months and of those, 74 (84%), had 6-minute walk data at both baseline and 6 months, and they showed an average improvement in distance walked of 150 meters. Overall, both quality of life and functional capacity showed improvements following HVAD implant.

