2.1. Sample Size Estimate and Justification

2.1.1. Sample Size

Success at 6 months is estimated to be 86% compared to a performance goal of 77.5%. Using an exact binomial test, with a one-sided alpha of 0.05, and 80% Power, a sample size of 145 implanted subjects is required.

The target success estimate of 86% is based on the following:

- The primary endpoint observed in the final BTT IDE Report for the more recent BTT CAP population (N=242), resulted in a success rate of 85.8% (205 out of 239 eligible subjects) for sternotomy subjects.

- Post-approval data from the INTERMACS Registry (through Q2 2014), indicates similar results for the sternotomy population of 88.0% (396/450) with a lower rate of success for the small subset of thoracotomy (83.3%, 55/66) and thoracotomy on-pump (82.6%, 38/46) subjects.
- The INTERMACS Federal Partners Report (from Q1 2014) indicates an 85% Kaplan-Meier survival estimate at 6 months. This is not the same as “success” in that post-exchange survival is considered.

Success will be met if the lower bound of the upper one-sided exact 95% confidence interval is greater than 77.5%.

The mean length of initial hospital stay is estimated to be 26.1 days with a standard deviation of 22.8 days and a median of 20 days based on data from the BTT CAP population (N=242). Using a one sample t-test, with a one-sided alpha of 0.05, a sample of 145 implanted subjects with an average value of 21.3 days or less will result in power greater than 80%.

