3.2. Definition of Calculated Variables

1. Basic Variable Definitions

- Age will be calculated as the informed consent date minus the date of birth divided by 365.24 [Age=(ICF Date-DOB)/365.24]. Age will be rounded down to the nearest whole number
- Body mass index (BMI; kg/m²) is calculated as: weight (kg) / [height (m)]², rounded to one decimal place.
- Body surface area (BSA; m²) is calculated as:
$$BSA = (W * H / 3600)^{0.5}$$
where W = weight in kg and H = height in cm
- Weight will be displayed in kilograms (kg), height will be displayed in centimeters (cm), and temperature will be displayed in Celsius (C).
- Weights, heights, or temperatures recorded in alternate units will be converted to the units being displayed using standard conversion formulas.
- Length of Operative Time (Hours) = Time end of surgery for implantation – Time start of surgery for implantation
- Length of Initial Hospital Stay (Days) = Date of discharge following device implantation – date of hospitalization prior to device implantation + 1
- For days on or after the device is implanted:
Relative Study Day (Rel Day) = Date of Assessment – date of induction of anesthesia to implant of the study device + 1.
For days before the device is implanted:
Relative Study Day (Rel Day) = Date of Assessment – date of induction of anesthesia to implant of the study device.
- Days survived = Date of death/date of event for censoring – date of induction of anesthesia to implant of the study device + 1

- Days of hospitalization = Date of hospital discharge – Date of admission + 1
- Cumulative days of hospitalization after initial hospitalization is the sum of length of hospital stays after initial hospitalization.
- Days to first explant = Date of explant – date of induction of anesthesia to implant the initial study device + 1
- Days to first exchange = Date of exchange – date of induction of anesthesia to implant the initial study device + 1
- Days to transplant = Date of transplant – date of induction of anesthesia to implant the initial study device + 1
- Change from baseline (CFB) = Visit value – Screening/Pre-Implant value

2. Calculation of adverse event rate per patient-year

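### The SAP defines initial length of stay in two incompatible ways and gives no readable rule for deaths before discharge, so an early death may count as a short stay

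*SAP*

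**What the plan says.** Two SAP sections define the same variable.

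- **SAP 2.4.2** covers all enrolled and implanted subjects. The stay is "calculated by considering the number of days in acute care (ICU/CCU) plus the number of days in intermediate/step-down care", both as reported by the registry. The same sentence describes the total as running from implant to discharge.
- **SAP 3.2** gives a date formula: "Length of Initial Hospital Stay (Days) = Date of discharge following device implantation", minus the date of the hospital admission before implantation, plus 1.

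Protocol 11.4 adds that "imputation for missing data regarding duration of hospital stay (in days) will not be performed".

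The benchmark is in SAP 2.1.1: "The mean length of initial hospital stay is estimated to be 26.1 days with a standard deviation of 22.8 days and a median of 20". It comes from the BTT CAP population (N=242). SAP 2.4.2 tests the mean against 26.1 days with a one-sided t-test at 0.05. A one-sample sign test supports it, which Protocol 11.2 sets against the 20-day median.

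No readable text says which definition governs, how a death before first discharge is scored, or how such deaths were handled in the CAP figures. The text under Protocol 11.1.3, parts of 11.4 and parts of SAP 2.4.7 are not visible.

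**The concern.** Apart from the primary endpoint this is the only endpoint with a formal test; SAP 2.4.3 makes the others descriptive. The hypothesis rewards a lower mean, so anything that shortens measured stay without benefit to the patient works towards success.

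Two things depend on which definition is programmed. The first is the start date. Pre-implant inpatient days count under 3.2 and not under 2.4.2, yet both would be compared with the same 26.1 days. The second is death before discharge. A subject who dies in the ICU on day 5 has about 5 registry care days, below the benchmark median, and so moves the result towards improvement under 2.4.2. Under 3.2 that subject has no discharge date and, without imputation, leaves the analysis. The sign test, included to handle skewness, is exposed to the same problem.

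**Working it through.** **The plan's own figure.** Inputs from SAP 2.1.1: N = 145, SD 22.8, null mean 26.1, target mean 21.3, one-sided alpha 0.05. The noncentrality is 4.8 / (22.8/√145) = 2.535 on 144 degrees of freedom, which gives power 81.0%. The stated power above 80% reproduces. Significance needs an observed mean of about 26.1 − 3.13 = 22.97 days.

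**Start date.** Assume the benchmark counts from implant and the true post-implant mean is 21.3 days. If the date formula adds 1 pre-implant day (assumed), the difference is 4.8 − 1 = 3.8 days and power is 64%. With 3 days it is 1.8 days and 24%. The documents give no figure for pre-implant days.

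**Deaths scored at their days in care, t-test.** Assumptions not in the documents: gamma stays with mean 26.1 and SD 22.8 for survivors (no true improvement), exponential death times with mean D, a share q of in-hospital deaths, and a survivors-only benchmark. The expected mean falls by q × (26.1 − D). Rejection rates are from 40,000 simulated trials of 145.

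| q | D | Fall in mean (days) | t-test false-positive rate |
|---|---|---|---|
| 0 | – | 0 | about 6.7% |
| 3% | 10 | 0.03 × 16.1 = 0.48 | about 11% |
| 5% | 10 | 0.05 × 16.1 = 0.81 | about 14% |
| 8% | 10 | 0.08 × 16.1 = 1.29 | about 20% |
| 5% | 20 | 0.05 × 6.1 = 0.31 | about 9% |

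The 6.7% base reflects skewness, not deaths. Dropping the deaths leaves the rate at about 6.7%.

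**Sign test.** At least 83 of 145 stays below 20 days are needed (size 4.8%). With mean death day 10, the chance that a death falls before day 20 is 1 − e^(−2) = 0.865. So P(stay < 20) = 0.5(1 − q) + 0.865q, which is 0.511, 0.518 and 0.529 at q = 3%, 5% and 8%. The exact binomial rates are 8.1%, 11.1% and 16.9%.

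**If the benchmark also counted deaths as short stays.** With the same rule and death rate, the survivors' mean consistent with 26.1 is (26.1 − 10q)/(1 − q), or 26.95 days at 5%. The t-test rate then stays at the no-death level, about 6.5% to 7%. With 3% deaths in the benchmark, the survivors' mean is (26.1 − 0.3)/0.97 = 26.6. With 8% deaths in the trial, the expected mean is 0.92 × 26.6 + 0.08 × 10 = 25.3 days, and the rate is about 14%.

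**The case against.** The strongest reply is that SAP 2.4.2 also describes its total as running to discharge. Both definitions could then require a discharge, or a death date could be entered as a discharge date. That stands in part: the treatment of deaths is the natural reading of each section, not something the SAP states. It does not touch the difference in start date.

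A second reply is that the CAP benchmark may have counted deaths in the same way, which would remove the bias. This also stands as a possibility. It needs similar early mortality as well as the same rule. Protocol 11.2 reports lower registry success for thoracotomy (83.3%) than for sternotomy (88.0%). Success is not in-hospital mortality, but equal mortality cannot be presumed.

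Third, the inputs matter. No in-hospital death rate is given, the mean death day of 10 is assumed, and deaths after a long ICU stay lengthen the mean. The 8% scenario exceeds total 180-day mortality in the earlier US trial (8/140 = 5.7%, Protocol 4.2.3).

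Three stronger readings are tempting, and the documents do not support them.

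- A reader might infer that early mortality would by itself produce a positive result. To bring the expected mean to 22.97 days, deaths on day 7 would have to reach 3.13 / (26.1 − 7) = 16%. Deaths are also failures on the primary endpoint, so they would not go unseen.
- A reader might take "A Discharge visit was conducted for 128 patients (median duration of hospital stays was 19 days"), against 140 implants, as evidence that the benchmark excludes deaths. That is the ADVANCE trial, not the CAP population, and the reasons for the 12 missing discharge visits are not given.
- A reader might assume that every in-hospital death falls before day 20, which gives sign-test rates of 9.7%, 14.4% and 24.2%. That contradicts the death-time assumption used for the t-test.

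**Conclusion.** The concern holds as a conflict between two definitions and a missing rule in the readable text. The start-date conflict is explicit. The conflict over deaths rests on the natural reading of each section.

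The possible inflation is material but conditional. The 11% to 20% range for the t-test requires a survivors-only benchmark and early deaths. It shrinks with later deaths, disappears when benchmark and trial share the rule and the death rate, and returns at about 14% if the trial has more early deaths than the benchmark (8% against 3%). These are illustrations of sensitivity, not estimates of the error rate in this trial. The point should be settled before analysis because the choice of definition can change the result of a formal test.

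**What to change.** 1. Keep one definition of initial length of stay in SAP 2.4.2 and 3.2, with the start date used for the CAP benchmarks.
2. State how a death before discharge is scored. Re-tabulate the CAP mean and median by that rule, or at least state how CAP deaths were counted.
3. Do not credit death before discharge as a short stay. In the supportive sign test count it as not improved, and rebuild the 20-day median by the same rule.
4. Run the t-test by the rule that matches the benchmark. Dropping trial deaths against a benchmark that includes them errs the other way: at 5% deaths averaging day 10, type I error falls to about 2.8%.
5. Add the discharged-alive mean as a sensitivity analysis, and report the number of in-hospital deaths beside it.

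The cost is SAP wording and one re-tabulation of CAP data, if those data are available to the sponsor; no new data collection is needed. A few subjects move from improved to not improved. If the median cannot be rebuilt, the sign test becomes conservative: with a survivors-only median and 5% deaths, P(improved) is 0.5 × 0.95 = 0.475, and the chance of 83 or more of 145 falls from 4.8% to about 1.2%.

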### **Secondary Endpoint:**

The mean length of initial hospital stay is estimated to be 26.1 days with a standard deviation of 22.8 days and a median of 20 days based on data from the BTT CAP population (N=242). Using a one sample t-test, with a one-sided alpha of 0.05, a sample of 145 implanted subjects with an average value of 21.3 days or less will result in Power greater than 80%.

Due to the skewed nature of this data, a non-parametric test (one-sample Sign test with a one-sided alpha of 0.05) to assess a reduction in median days (from the estimated 20 days) will also be conducted for support.

For exploratory purposes, the secondary endpoint will also be assessed and observed by:

- Site
- CPB (on pump, off pump)

- Outflow location

The sample size calculations were performed using nQuery Advisor®.

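### SAP 2.4.2 names an upper-tail t-test for length of stay, but its own alternative hypothesis and power figure require the lower tail

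*SAP*

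**What the plan says.** SAP 2.4.2 opens with "The secondary endpoint is improvement in the length of initial hospital stay". It sets H0: μ_T ≥ 26.1 against Ha: μ_T < 26.1, with μ_T defined as the mean initial stay under the thoracotomy technique. It then says the endpoint will be tested "using an upper tail one-sided t-test at 0.05 level of significance". Because the data are skewed, "a one-sample sign test with an upper tail one-sided level of confidence of 0.05 will be conducted as supportive analysis".

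SAP 2.1.1 gives the planning basis: a benchmark mean of 26.1 days "with a standard deviation of 22.8 days and a median of 20 days", a one-sample t-test at one-sided alpha 0.05, and the statement that "a sample of 145 implanted subjects with an average value of 21.3 days or less will result in power greater than 80"%.

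Protocol 11.2 describes the same supportive test as a "one-sample Sign test with a one-sided alpha of 0.05", used "to assess a reduction in median days (from the estimated 20 days) will also be conducted for support". The protocol's study summary says the same.

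**The concern.** The hypotheses and the test sentence stand a few lines apart in SAP 2.4.2 and point in opposite directions. The hypotheses are written on the mean stay itself, so the upper tail is the tail of long stays. It would be the right tail only if the statistic were built on a reversed difference such as 26.1 minus the mean, and the SAP defines none.

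This is the SAP's decision rule for the trial's only secondary endpoint. A program or table written from the test sentence alone would return the complement of the intended p-value, so a trial that met its own target would appear to have failed. If the error were noticed only after results were seen, changing the tail would invite the charge that it was changed to suit the data.

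**Working it through.** **Inputs.** n = 145, benchmark mean 26.1, SD 22.8, planning mean 21.3, one-sided alpha 0.05 (SAP 2.1.1); hypotheses and tail (SAP 2.4.2); null median 20 days and direction of the sign test (Protocol 11.2).

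**1. Reproduce the plan's power figure.**
- Standard error = 22.8/√145 = 1.8934; df = 144; critical t = 1.6555.
- Noncentrality at a true mean of 21.3 = (21.3 − 26.1)/1.8934 = −2.535.
- Lower tail, P(T < −1.6555) from the noncentral t: **81.0%**. The normal approximation gives 81.3%.
- Lower-tail power is exactly 80% at a true mean of 26.1 − 4.73 = 21.37 days, which fits the SAP's threshold of 21.3 days or less.

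The plan's figure is therefore right, and it is a lower-tail figure.

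**2. Apply the tail as written.**
- Upper tail, P(T > 1.6555) with the same noncentrality: 0.0000154, or **0.0015%**.
- By symmetry, the upper-tail test would reject with 81.0% probability if the true mean were 26.1 + 4.8 = 30.9 days.

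**3. Rejection regions for the observed mean (at SD 22.8).**

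| Tail | Rejects H0 when the observed mean is |
|---|---|
| Lower | below 26.1 − 1.6555 × 1.8934 = 22.97 days |
| Upper | above 26.1 + 1.6555 × 1.8934 = 29.23 days |

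**4. A trial that observes exactly 21.3 days.**
- t = −4.8/1.8934 = −2.535.
- Lower-tail p = 0.006; upper-tail p = 0.994.
- Upper one-sided 95% confidence bound for the mean = 21.3 + 1.6555 × 1.8934 = 24.43 days, below 26.1, in agreement with the lower-tail result.

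**5. The sign test.** Take 145 stays, none equal to 20 days. Under a null median of 20, the count X on either side is Binomial(145, 0.5).
- P(X ≤ 62) = 0.0482 and P(X ≤ 63) = 0.0673, so 62 is the largest count above 20 days that rejects in favor of a shorter median.
- 145 − 62 = 83, and P(X ≥ 83) = 0.0482. Rejecting for 62 or fewer stays above 20 days is the same test as rejecting for 83 or more below it.

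The upper-tail label is therefore correct if short stays are counted and wrong if long stays are counted. SAP 2.4.2 does not say which.

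**6. Sensitivity of that cut-off to the number of non-tied stays.** It falls to 59 at 140 and 57 at 135. Keeping 62 there would give a size of about 0.10 and 0.19.

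**The case against.** The strongest reply is that nobody would be misled. Ha is printed just above the test sentence, the endpoint is described as an improvement, and a p-value of 0.994 beside a mean 4.8 days under the benchmark would be questioned at once. It can be added that SAP 2.1.1 names no tail, so its power figure only restates the direction in Ha. Most of this stands, and it limits the weight of the point. It does not make the sentence correct: a decision rule should not depend on the programmer overriding it, and the power figure does confirm which of two conflicting statements was planned.

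A reader might infer that the error could produce a false claim of shorter stay. The documents do not support that. The literal test rejects only for long stays, and Ha and the protocol's stated aim of a reduction leave no doubt about what counts as benefit. The slip works against the sponsor's claim.

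A reader might also infer that the sign test has the wrong tail, that the plan gives it no null value or direction, or that two analysts could reach opposite conclusions from it. None of these holds. Protocol 11.2 and the study summary fix a reduction from a median of 20 days at one-sided alpha 0.05. Once the direction is fixed, counting above or below 20 days is the same test (step 5). What remains is that SAP 2.4.2 does not carry these details over and calls 0.05 a level of confidence where a significance level is meant.

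Protocol 11.1.3, the protocol's own secondary-endpoint section, has no readable text in the public copy. It may state the test rule correctly, so this point rests on the SAP sentence alone.

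**Conclusion.** The t-test sentence in SAP 2.4.2 is wrong as written. It names the tail opposite to its own alternative hypothesis and to the direction in which SAP 2.1.1 has 81.0% power; in the named tail, power at 21.3 days is 0.0015%. These figures assume n = 145, an SD of 22.8 days and a statistic built on the mean stay minus 26.1. The intent is not in doubt and the endpoint is secondary, so this is a drafting error that should be corrected before the analysis is programmed. It is not a flaw in the design. The sign-test part is minor: detail missing from the SAP but present in the protocol, plus one wrong term.

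**What to change.** In SAP 2.4.2, replace the description of the t-test with: *lower-tail one-sided t-test at the 0.05 significance level (reject H0 if the upper one-sided 95% confidence bound for the mean is below 26.1 days)*.

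As a minor accompanying edit, align the sign-test sentence with Protocol 11.2: *one-sample sign test of H0: median ≥ 20 days versus Ha: median < 20 days at one-sided significance level 0.05, with the exact binomial p-value computed on the non-tied stays actually observed*. This removes both the tail label and the level-of-confidence wording.

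No fixed count should be written in. Stays are whole days and can tie at 20, Protocol 11.4 does not impute missing stays, and Protocol 7.2 allows enrollment above the required sample size, so the number of non-tied stays is unlikely to be exactly 145.

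The cost is two sentences in one SAP section. Sample size, planned power and data collection are unchanged, and the wording uses only the sponsor's own hypotheses, null median and alpha, apart from making the handling of ties explicit.
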